5.12. Analyses of Biomarkers

5.12.1. Analyses of Biomarkers

Descriptive statistics for the observed values, change and percent change from Day 1 of current study, change and percent change from baseline of parent study by visit will be summarized for all patients in SAF. It will be provided for the following biomarker variables:

- TARC
- total serum IgE
- hs-CRP,
- anti-TPO

Corresponding figures will be provided.

Correlation of baseline TARC (measured value) and baseline IgE (measured value) of current study with the following categorical clinical endpoints at each visit will be explored for patients without prior experience to dupilumab in the parent studies (i.e. dupilumab naïve patients). Subgroup analysis of these endpoints by baseline value tertiles (≤ 33 rd percentile, $< 33 - \leq 67$ th percentile, > 67 th percentile) will be provided.

- IGA 0-1
- EASI-75 relative to baseline of current study
- Proportion of patients with improvement (reduction) of pruritus NRS ≥ 4 from baseline of current study
- Proportion of patients with improvement (reduction) of pruritus NRS ≥ 3 from baseline of current study

Correlation of baseline TARC (measured value) and IgE (measured value) of current study with the following continuous clinical endpoints will be explored using the Spearman's rho test for patients without prior experience to dupilumab in the parent studies (i.e. dupilumab naïve patients). Both Spearman correlation coefficients and p-value will be reported.

- Percent change from Day 1 of current study in EASI score
- Percent change from Day 1 of current study in weekly pruritus NRS

Shift tables from baselines status to post-baseline status for ANA, anti-TPO and anti-dsDNA will be provided.

All above analyses will be performed on the SAF for all observed data. No missing data will be imputed.

5.12.2. “Normalization” Biomarker Data Related Evaluations

The additional analysis will be performed on the following biomarkers to evaluate the proportion of patients for whom biomarker concentrations “normalize” (shift from above normal to within the normal range) at each visit.

- Total IgE
- TARC

These evaluations will be done using two subsets of the SAF specifically defined as below:

- Include patients with the elevated total IgE, or TARC at baseline of current study. Patients in SAF with a normal (below the ULN) serum biomarker level at Day 1 of current study will be excluded from the analysis for that biomarker, and
- Include patients with the elevated total IgE, or TARC at baseline of parent study. Patients in SAF with a normal (below the ULN) serum biomarker level at baseline of parent study will be excluded from the analysis for that biomarker, and

These patients should also have at least one post-Day 1 of current study measurement and received treatment.

Therefore, the analysis population for each of the biomarkers of interest will vary depending on the number of SAF patients meeting “elevation” criteria at baseline. All observed biomarker data without imputation for missing value will be used for this analysis. Summary tables with normal/elevated status for total IgE, and TARC at baseline and each post-baseline visit (until end-of-study) will be provided.

Method for Determining a ULN for Total IgE

Total IgE are established clinical assays; the upper limit of normal (ULN) from the central lab reference range will determine the threshold for normal vs. elevated status. The reference ranges for the total IgE ([Phadia AB 2014](#)) are specified in below table, from the product inserts provided by the manufacturer of the assays.

Allergen (Analyte)	Phadia Code	Catalog #	Reference Range
Allergen Total IgE		14-4509-01	0-119 kU/L for both adult sexes

Method for Determining a ULN for TARC

A standard reference range for TARC in healthy adult populations has not been established. To determine an appropriate ULN for these analyses, a literature review was conducted to identify summary estimates of TARC in healthy adult volunteers, in studies using identical methodology (ELISA, R&D Systems, Minneapolis) to measure serum TARC levels (pg/mL). Two comparable studies were identified and estimates are provided in [Table 3](#). Along with these estimates, data from a FIH Study (R668-AS-0907) was included to supplement available information and ensure

consistency across internally and externally obtained measurements of serum TARC. The R668-AS-0907 study comprised healthy volunteers and the TARC measurements provided in [Table 3](#) were obtained at Day 1, prior to administration of study drug or placebo.

From the two external and one internal estimates, a combined mean and SD were calculated (using the study healthy volunteers sample size as weights). The mean combined serum TARC level + two standard deviations was used to determine the ULN. After combining data across studies, the calculated ULN for serum TARC is 1081.5 pg/mL. Under the assumption that serum TARC levels are normally distributed in healthy adults, approximately 95 percent of normal serum TARC levels will fall within this range. From the summary data identified by literature review, as well as our internal data, serum TARC levels in healthy adults appear to have a slight right skew. However, for the purposes of this analysis, the normal distribution assumption should provide a more conservative estimate of the ULN (in comparison to using 95th percentile or maximum study measurements), thereby increasing the burden of establishing normalization of serum TARC levels in our patient population. Additionally, from internal study R668-AS-0907, the 90 - 95 percentile for TARC at Day 1 was 1042 – 1142 pg/mL, consistent with the calculated ULN (percentile information from external sources was not available).

Table 3: External/Internal Reference Estimates of TARC

Sample Type	Detection Method	Healthy Controls			Reference
		Sample Size	Mean	Standard Deviation	
Serum	ELISA (R&D, Minneapolis USA)	48	616	290.6	Internal REGN Study: R668-AS-0907
Serum	ELISA (R&D, Minneapolis USA)	44	437.9	292	K. Jahnz-Rozyk, et al, "Serum thymus and activation-regulated chemokine, macrophage derived chemokine and eotaxin as markers of severity of atopic dermatitis." Allergy 2005; 60: 685–688
Serum	ELISA (R&D, Minneapolis USA)	20	258	123	Caproni M, et al; "Serological detection of eotaxin, IL-4, IL-13, IFN-g, MIP-1a, TARC and IP-10 in chronic autoimmune urticaria and chronic idiopathic urticaria." J Dermatol. Science (2004) 36, 57-59
COMBINED:		112	482.1	299.7	ULN: 1081.5 (482.1+2*299.7)

6. DATA CONVENTIONS

The following analysis conventions will be used in the statistical analysis.

6.1. Definition of Baseline for Efficacy/Safety Variables

Unless otherwise specified, the baseline assessment for all measurements will be the latest available valid measurement taken prior to the first administration of study drug in the current study. The following rules specify the determination by both date/time information:

1. For the AE, lab (including biomarker), PK and ADA data, both date and time of the measurement will be used to determine baseline by comparing with the first injection date and time.
2. For other data except AE, lab (including biomarker), PK or ADA, only date of the measurement will be used to determine baseline by comparing with the first injection date.

The baseline value of parent study is defined as the baseline value a patient had prior to the first dose in the parent study. For patients who have been screened for a phase 3 study (R668-AD-1334 or R668-AD-1416), but could not be randomized because of randomization closure, the initial baseline value of the parent study will be the last nonmissing value during the screening period in the parent study.

6.2. General Data Handling Conventions

For the laboratory safety variables and biomarker data, if the data are below the lower limit of quantification (LLOQ) / limit of linearity, then half of the lower limit value (i.e., LLOQ/2) will be used for quantitative analyses. For data above the upper limit of quantification (ULOQ) / limit of linearity, the upper limit value (i.e., ULOQ) will be used for quantitative analyses.

6.3. Data Handling Convention Missing Data

Missing data will not be imputed in listings. This section includes the methods for missing data imputation for some summary analyses, if necessary.

Adverse event

If the intensity of a TEAE is missing, it will be classified as “severe” in the frequency tables by intensity of TEAE. For example, if the assessment of relationship of a TEAE to the investigational product is missing, it will be classified as “related” in the frequency tables by relation to the investigational product.

Adverse event start date

AE start date will be used for AE classification and analysis of AESIs. If AE start date is not complete, then the character variable will keep the original incomplete date, the numerical date variable will be imputed and an imputation flag will indicate which date component is missing.

If AE start day is missing, and AE start month and year are not missing: If AE start year is the same as first dose year and the AE start month is the same as the first dose month) then impute AE start day using the day of first dose. If this leads to a date after the AE end date, use AE end date instead. Otherwise impute the AE start day using the first day of the month. If this leads to a date before informed consent, the informed consent date will be used. Imputation flag is 'D'.

If AE start month is missing, and AE start year is not missing: If AE start year is less than the first dose year, use the informed consent day and month. If AE start year is equal to the first dose year, use the first dose day and month. If this leads to a date after the AE end date, use AE end date instead. If AE start year is after the first dose year, use 01 January. Imputation flag is 'M'.

If AE start year is missing: Impute AE start date using the day of first dose. If this leads to a date after the AE end date, use AE end date instead. Imputation flag is 'Y'.

Adverse event end date

The general recommendation is not to impute AE end date. However, since AE end date will be used for AE starting date imputation, In order to carry through the logic for programming, the following intermediate step will be used. Afterwards, only the original character/numeric date recorded in CRF will be kept in the final analysis dataset.

If AE end day is missing, and AE end month and year are not missing: Impute AE end date using the last day of the month. If this leads to a date after end of study follow up date, use end of follow up date instead.

If AE end month is missing, and AE end year is not missing: Impute AE end date using 31 December as the day and month. If this leads to a date after end of study follow up date, use the end of follow up date instead.

If AE end year is missing: Impute AE end date using the end of follow up date.

Medication start and end date missing

To determine whether a medication is pre-treatment medication or concomitant medication or both, the missing medication start date is estimated as early as possible, and the missing medication end date is estimated as late as possible. If the medication start date is missing, the onset day will not be calculated in medication listings.

Prior medication start date

If start day is missing, and start month and year are not missing: Impute the start day using the first day of the month. Imputation flag is 'D';

If start month is missing, and start year is not missing: Impute the day and month using 01 January. Imputation flag is 'M'.

If start year is missing: Impute start date using 2 years before inform consent date. Imputation flag is 'Y'.

A special note: for start date with year missing, the general principle is not to impute. However in order to simplify the programming flow, the imputation is proposed to inline with the protocol which specifies to collect up to 2 years prior medication. Since the start date of prior medication will not be used in any analysis, the rule will not impact the analysis result.

Prior medication end date

If end day is missing, and end month and year are not missing: Impute end date using the last day of the month. If this leads to a date on or after first dose intake date, use first dose intake date -1 instead. Imputation flag is 'D'.

If end month is missing, and end year is not missing: Impute end date using 31 December as the day and month. If this leads to a date on or after first dose intake date, use first dose intake date -1 instead. Imputation flag is 'M'.

If end year is missing: Impute end date using the first dose intake date -1. Imputation flag is 'Y'.

Concomitant medication start date

The imputation rule for concomitant medication start date is the same as AE start date.

Concomitant medication end date

If end day is missing, and end month and year are not missing: Impute end date using the last day of the month. If this leads to a date after end of study follow up date, use end of follow up date instead. Imputation flag is 'D'.

If end month is missing, and end year is not missing: Impute end date using 31 December as the day and month. If this leads to a date after end of study follow up date, use the end of follow up date instead. Imputation flag is 'M'.

If end year is missing: Impute date using the end of follow up date. Imputation flag is 'Y'.

Medication coding

Medications whose ATC level 4 cannot be coded will be summarized by setting ATC4=ATC2 in the table programs. However, these uncoded ATC level 4 records still need to be confirmed with study DM and study MD.

PCSV

Patients who had post-baseline PCSV but missing baseline value will be regarded as having treatment emergent PCSV.

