**9.6. Additional Statistical Data Handling Conventions**

The following analysis and data conventions will be followed:

Definition of baseline:

- The baseline assessment will be the latest, valid predose assessment available.

General rules for handling missing data:

- If the start date of an AE or concomitant medication is incomplete or missing, it will be assumed to have occurred on or after the intake of study medication, except if an incomplete date (eg, month and year) clearly indicates that the event started prior to treatment. If the partial date indicates the same month or year of the intake of study medication date, then the start date by the study medication intake date will be imputed, otherwise, the missing day or month by the first day or the first month will be imputed.
- No imputations for missing laboratory data, electrocardiogram data, vital sign data, or physical examination data will be made.

Visit windows:

- Assessments taken outside of protocol allowable windows will be displayed according to the CRF assessment recorded by the investigator.

Unscheduled assessments:

- Extra assessments (laboratory data or vital signs associated with non-protocol clinical visits or obtained in the course of investigating or managing AEs) will be included in listings, but not summaries. If more than 1 laboratory value is available for a given visit, the first observation will be used in summaries and all observations will be presented in listings.

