4.6. Safety Variables

4.6.1. Adverse Events and Serious Adverse Events Variables

The primary endpoint in the study is the incidence and rate (events per patient-year) of treatment-emergent adverse events (TEAEs) through the last study visit.

The key secondary endpoints related to AE is

- Incidence and rate (events per patient-year) of SAEs and AEs of special interest

Adverse events and serious adverse events will be collected from the time of informed consent signature and then at each visit until the end of the study. All adverse events are to be coded to a “Preferred Term” and associated primary “System Organ Class (SOC)” according to the Medical Dictionary for Regulatory Activities (MedDRA, latest version).

An **Adverse Event** is any untoward medical occurrence in a patient administered a study drug which may or may not have a causal relationship with the study drug. Therefore, an AE is any unfavorable and unintended sign (including abnormal laboratory finding), symptom, or disease which is temporally associated with the use of a study drug, whether or not considered related to the study drug.

AEs also include: any worsening (i.e., any clinically significant change in frequency and/or intensity) of a pre-existing condition that is temporally associated with the use of the study drug; abnormal laboratory findings considered by the investigator to be clinically significant; and any untoward medical occurrence.

A **Serious Adverse Event** is any untoward medical occurrence that at any dose results in death; is life-threatening; requires in-patient hospitalization or prolongation of existing hospitalization; results in persistent or significant disability/ incapacity; is a congenital anomaly/ birth defect; or is an important medical event.

The criteria for determining whether an abnormal laboratory, vital sign or ECG finding should be reported as an AE are as follows:

- Test result is associated with accompanying symptoms, and/or
- Test result requires additional diagnostic testing or medical/surgical intervention, and/or
- Test result leads to a change in dosing (outside of protocol-stipulated dose adjustments) or discontinuation from the study, significant additional concomitant drug treatment, or other therapy

The pre-treatment period is defined as the period from the subject providing informed consent up to the first dose of study drug in current study.

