Hence any AE with an onset between the end of study visit under protocol amendment 6 and the date of first injection under amendment 7; or between end of study visit under protocol amendment 7 and date of first injection under amendment 8 is **not** considered TEAEs.

The list of adverse events of special interest (AESI) was revised several times. Below is the AESI list under protocol amendments 4 and 5:

- Anaphylactic reactions
- Acute allergic reaction
- Severe injection site reactions that last longer than 24 hours
- Mycosis fungoides
- Cutaneous T-cell dyscrasia
- Any severe infection
- Any infection requiring treatment with parenteral antibiotics
- Any infection requiring treatment with oral antibiotics/anti-viral/anti-fungal for longer than 2 weeks
- Any clinical endoparasitosis
- Any opportunistic infection

Under protocol amendment 6, suicide-related events and certain eye-related events were added as AESIs. Under protocol amendment 7, the list of AESI are as follows:

- Anaphylactic reactions
- Systemic or extensive hypersensitivity reactions
- Malignancy (except basal cell carcinoma)
- Helminthic infections
- Any suicide-related events
- Any type of conjunctivitis or blepharitis, or keratitis (severe or serious)

The SAP summarizes AESIs according to the most current list under protocol amendments 7 and 8. The definition of AESI is same under protocol amendment 7 and 8.

[Appendix 10.6](#) provides a list of AESIs search criteria.

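### SAP 6.3 has no rule for a missing AE start day in the month of re-entry, so a few events that began after re-injection can be dated into the off-study gap and lost as TEAEs

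*SAP*

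**What the plan says.** SAP Section 6.3 deals with a missing start day in two branches. The first applies "If AE start year is the same as first dose year and the AE start month is the same as the first dose month", and imputes the day of first dose, capped at the AE end date. The second covers every other month: "Otherwise impute the AE start day using the first day of the month", moved to the consent date if it would fall before consent. The section adds that "AE start date will be used for AE classification and analysis of AESIs", so the imputed date decides whether an event is a TEAE.

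SAP Section 4.6.1 ends the pre-treatment period with the words "up to the first dose of study drug in current study", which ties first dose to Day 1 of this study. For re-entry the same section speaks of first injection under a given amendment. It takes an AE out of the TEAE set when the event has "an onset between the end of study visit under protocol amendment 6 and the date of first injection under amendment 7". A second exclusion does the same for the later gap, from the amendment 7 EOS visit until dosing restarts under amendment 8. Onsets during treatment or follow-up are TEAEs.

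Protocol Section 9.6 says of an incomplete or missing start date that "it will be assumed to have occurred on or after the intake of study medication", unless the partial date clearly shows an earlier start. It then gives the working rule: the intake date if the month or year matches, otherwise the first day or first month.

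**The concern.** The SAP created an interval in which AEs do not count, but left unchanged the rule that places partially dated AEs in time. SAP Table 1 lists the sections revised for the gaps: exposure and compliance, the TEAE definition, and visit windows. Section 6.3 is not among them.

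The month of first dose is protected because day 1 of that month would push on-treatment events into the pre-treatment period. The month of re-injection has the same structure, with off-study time before the injection and treatment after it, but it has no protection.

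An event moved into the gap leaves the primary endpoint count, the AESI tables and the NEPY and EAIR numerators of SAP Appendix 10.5. The patient's time after re-injection stays in the denominators. The days concerned are those just after re-exposure. Immunogenicity on re-treatment is a secondary objective, and SAP Section 5.11.3 looks at hypersensitivity and anaphylaxis during the TEAE period.

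**Working it through.** The plan gives no figure to reproduce here, so the check applies its rules directly.

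**1. When an event is lost.** Take an AE that truly began on or after re-injection, in the re-injection month, with the day missing. Section 6.3 dates it to the 1st. Section 4.6.1 excludes it if EOS < onset < re-injection. It is therefore lost only if EOS was before the 1st and re-injection was after the 1st. Illustrative dates:

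| EOS visit | Re-injection | AE start recorded | Imputed | Result |
|---|---|---|---|---|
| 24 May 2017 | 18 Jul 2017 | Jul 2017 | 1 Jul 2017 | Not a TEAE |
| 5 Jul 2017 | 18 Jul 2017 | Jul 2017 | 1 Jul 2017 | TEAE (follow-up) |
| None, resumed in follow-up | 18 Jul 2017 | Jul 2017 | 1 Jul 2017 | TEAE (follow-up) |

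The consent fallback does not rescue the first case. Consent at study entry is years earlier. If re-consent is meant, it is taken at the re-entry visit, and dosing resumes at a later scheduled visit (Protocol Section 6.2.10 and Table 7, footnote r).

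**2. Share of such events lost.** Re-injection dates were enumerated over 2 Jun to 31 Dec 2017 (amendment 7) and 4 Jan to 30 Jun 2018 (amendment 8), evenly spread. True onsets were spread evenly from re-injection to month end. Both spreads are assumptions.

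| Days from EOS to re-injection | Share lost |
|---|---|
| 3 | 10–12% |
| 7 | 33–34% |
| 14 | 64% |
| 21 | 84% |
| 28 | 94% |
| 35 or more | 95% |

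The share stays below 100% because a re-injection on the 1st coincides with the imputed date. The longest off-study intervals follow from SAP Section 2.3: 33 − 16 = 17 weeks for the first gap and 21 − 12 = 9 weeks for the second. Averaged over an assumed uniform interval up to those limits, the share is about 86% and 79%.

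**3. Patients exposed.** SAP Section 2.3 gives about 113 patients in the first gap (median 17 weeks, follow-up 16 weeks) and about 272 in the second (median 10 weeks, follow-up 12 weeks).

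- First gap: the median just exceeds follow-up, so roughly half or somewhat more passed EOS: 113 / 2 ≈ 57.
- Second gap: the median is below follow-up, so fewer than half did: under 272 / 2 = 136.
- Together about 57 + 136 = 193 patient-gaps. 193 / 2678 enrolled ≈ 7%, with possible overlap between the gaps.

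**4. Events lost.** With re-injection evenly spread, about half of the month follows it.

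- Effective time: (57 × 0.86 + 136 × 0.79) × 0.5 ≈ 78 patient-months.
- Low: 78 × 0.15 × 0.02 ≈ 0.2 events.
- High: 78 × 0.20 × 0.10 ≈ 1.6 events.

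The rates of 0.15 to 0.2 AEs per patient-month and 2 to 10% of dates lacking a day are assumptions.

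**5. After the fix.** In the first example the AE is dated 18 Jul 2017 and stays a TEAE. The loss from the day-missing rule falls to zero.

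**The case against.** The other side has several sound points.

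- **The protocol does not contradict the SAP.** A reader who stops at the first sentence of Protocol Section 9.6 might infer an opposite default. The same bullet ends in the same first-of-month rule, and it does not mention re-entry. Only its stated principle, on treatment unless the date clearly shows otherwise, points towards the fix.
- **The first-of-month rule is not biased one way throughout.** In the EOS month, an AE that truly began after the EOS visit is set to the 1st, usually within follow-up, and is counted. A missing year goes to the first dose day, and so does a missing month in the first-dose year; both can add TEAEs. The downward direction holds only within the re-entry month.
- **Not every AE dated by month only in the re-entry month is lost.** AEs that truly began between the 1st and re-injection are correctly excluded under Section 4.6.1, and a short off-study interval often leaves EOS in the same month.
- **The events of most concern are the least likely to lack a day.** SAEs and AESIs must be entered within 24 hours of identification (Protocol Sections 7.2.2 and 7.2.3). The SAP also keeps the partial date and an imputation flag, so affected records can be traced.
- **The study is descriptive.** One or two events among 2678 patients will not visibly move a rate, and a patient leaves the incidence count only if they had no other TEAE.

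All of this limits the size and reach of the point. None of it supplies a rule for the re-entry month or keeps the event in the TEAE set. The SAP's neighbouring conventions are conservative (missing intensity counts as severe, missing relationship as related), so this outcome does not look intended.

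**Conclusion.** The point holds as a narrow gap in specification. It requires four things together: only the day is missing, the patient had an EOS visit and then re-entered, that visit was before the 1st of the re-injection month, and re-injection was after the 1st. An AE that began after re-injection is then classed as off-study, which is anti-conservative for the primary safety endpoint in the weeks after re-exposure.

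The likely size is about 0.2 to 1.6 events. It rests on the assumed AE and partial-date rates, on evenly spread dates and off-study intervals, and on about 190 patient-gaps inferred from medians. A reader might take 190 as a ceiling. It is not one, because the first-gap share may exceed half. The documents give neither the number of patients who re-entered after EOS nor the number of partial dates. No overall conclusion of the study depends on this. It is worth correcting because a single serious or hypersensitivity event after re-exposure would matter and the correction is easy.

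**What to change.** Add a branch to SAP Section 6.3 for AEs. If the day is missing, and the month and year match those of the first injection under amendment 7 or 8 after an EOS visit, impute that injection date, or the AE end date if earlier, unless available dates clearly show an earlier onset. List every imputed AE that falls in an off-study gap. Concomitant medication start dates now follow the AE rule, so state whether they follow this change too.

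The branch should stay confined to the re-entry month. A general rule moving every ambiguous date into treatment or follow-up would change classifications well beyond this problem.

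The cost is a short addition to the text, one branch in the program and one listing. Protocol Section 9 allows the SAP to be revised before database lock, and SAP Section 7 foresees an addendum for future analyses. The downside is that a few AEs that truly began in the gap may be counted as TEAEs, which is the conservative direction for safety.
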